## 9.2 Comparable Methods

The methodology described above are those previously used (see details above), and the resulting data will be able to be compared to existing data.

## 10. SPECIMEN MANAGEMENT

### 10.1 Laboratories

**The laboratory of [name] MD at the Center for Esophageal Research, Baylor Scott & White Research Institute, Dallas, TX** will serve as the biomarker laboratory for assessment of the primary biomarker (differences in the change of CDX2 mRNA levels from baseline to 12 months post-randomization in esophageal squamous tissue between participants taking aspirin supplementation versus those taking placebo) and two important secondary biomarkers (differences in the change of CDX2 mRNA levels from baseline to 18 months post-randomization in esophageal squamous tissue between participants taking aspirin supplementation versus those taking placebo and differences in the activation status of NF-kB by assessing levels of total and phospho-p65 and cytoplasmic to nuclear translocation of phospho-p65. [name] research has focused on the pathogenesis of reflux esophagitis, BE and esophageal adenocarcinoma. For the past 19 years, she has worked closely with [name] to establish a translational research program at the Dallas VA that incorporates cell culture models, animal models, and *in vivo* patient studies to answer research questions related to GERD, BE, and esophageal

adenocarcinoma. [name] and [name] in her laboratory will provide expertise in molecular and cell biology as well as our technical experience in investigating the role of phospho-p65 and CDX2 as biomarkers in esophageal squamous in predicting the recurrence of Barrett's metaplasia after radiofrequency ablation.

**Differences in the the prostanoid marker, prostaglandin E2, and prostaglandin synthases and Differences in the expression of proinflammatory cytokines known to induce activation of NFκB, i.e., TNFα, IL-1β, IL-6, IL-10, IL-17A, IL-23** will be measured in the laboratory of [name] Ph.D. at the University of Texas MD Anderson Cancer Center. [name] lab have developed highly sensitive and specific methods for the analysis of both endogenous and exogenous bioactive lipids, such as prostaglandins, leukotrienes and HETEs, derived from cyclooxygenase and lipoxygenase enzymes. These methods have been applied to *in vitro* and *in vivo* studies in support of cancer research already used extensively by numerous investigators nationally. [name] served as a leader of Analytical Core for the P01 project, led by [name] to understand the role of bioactive lipid in inflammation and cancer and her lab helped analyze eicosanoids levels in over 2000 samples in various biological matrices. The methodology for these analyses is based primarily on an LC/MS/MS method using stable isotope dilution techniques employing deuterated internal standards (IS). The eicosanoid analyses are routinely carried out by [name] laboratory. Additionally, the availability of the methods to simultaneously quantify COX and LOX metabolites has allowed a number of studies to illustrate the interrelationship of COX and LOX metabolites in certain malignancies.

## 10.2 Collection and Handling Procedures

### Research Mucosal Biopsy Specimens

[figure not shown]
Esophageal mucosa biopsy techniques have been described in Section 7. Types of assay conducted for each biopsy specimen are described in Section 8. Research biopsies will be obtained at baseline (after consent but prior to randomization), at 12 months and at 18 months as described in Section 7.

#### **Endoscopic research biopsies will be obtained with the Boston Scientific Radial Jaw**

**RJ4 large capacity biopsy forceps** (provided by coordinating center at no additional cost to participating sites) from 1 cm above the level of the lower esophageal sphincter, just above the proximal margin of the gastric folds, in a zone corresponding to the middle of the former Barrett's segment, and a zone 2 cm above the upper extent of the former Barrett's segment.

Tissue kits will be provided by the coordinating Center at the University of Texas MD Anderson Cancer Center. Tissue collection, handling, and shipping instructions will be included with each kit. Participating Sites may obtain tissue kits by faxing the Supply Order Form to the number provided (found in the Forms Packet). At least two weeks should be allowed to receive the shipping kits. Kits will be sent via FedEx ® at no additional cost to the participating institutions. They will not be forwarded by FedEx ® rush delivery service unless the participating institution provides their own FedEx ® account number or alternate billing number for express service. Because charges are incurred for all outgoing kits, a small, but sufficient, supply of the specimen collection kits should be ordered prior to participant entry.

**Barretts Participants**

Biopsy #	Planned Use
Level 1 (1 cm above GE junction)	
Biopsy A1 (Formalin fixed)	Histological evaluation and immunohistochemistry
2 Biopsy A2 (RNAlater®)	CDX2 mRNA
2 Biopsies A3 (Flash Frozen)	CDX2 mRNA
Biopsy A4 (Flash Frozen)	total and phospho-p65 and cytoplasmic to nuclear translocation of phospho-p65
Biopsy A5 (Flash Frozen)	PGE2 and proinflammatory cytokines
Biopsy A6 (Flash Frozen)	PGE2 and proinflammatory cytokines
Biopsy A7 (Flash Frozen)	PGE2 and proinflammatory cytokines
Level 2 (middle of former Barrett's segment)	
Biopsy B1 (Formalin fixed)	Histological evaluation and immunohistochemistry
2 Biopsies B2 (RNAlater®))	CDX2 mRNA
2 Biopsies B3 (Flash Frozen)	CDX2 mRNA
Biopsy B4 (Flash frozen)	total and phospho-p65 and cytoplasmic to nuclear translocation of phospho-p65
Biopsy B5 (Flash frozen)	PGE2 and proinflammatory cytokines
Biopsy B6 (Flash Frozen)	PGE2 and proinflammatory cytokines
Biopsy B7 (Flash Frozen)	PGE2 and proinflammatory cytokines
Level 3 (2 cm above former Barrett's segment)	
Biopsy C1 (Formalin fixed)	Histological Evaluation
2 Biopsies C2 (RNAlater®)	CDX2 mRNA
2 Biopsies C3 (Flash Frozen)	CDX2 mRNA
Biopsy C4 (Flash Frozen)	total and phospho-p65 and cytoplasmic to nuclear translocation of phospho-p65
Biopsy C5 (Flash Frozen)	PGE2 and proinflammatory cytokines

Biopsy C6 (Flash Frozen)	PGE2 and proinflammatory cytokines
Biopsy C7 (Flash Frozen)	PGE2 and proinflammatory cytokines

Biopsies A1, B1 and C1 will be placed in neutral buffered formalin at room temperature. Biopsies A2, B2 and C2 will be placed in RNAlater® at 2°-8°C. The remainder of the biopsies will be washed in phosphate buffered saline, each biopsy placed in a cryovial then placed in liquid nitrogen. Vials will be stored at a temperature of -80°C. Specimens must not be thawed before analysis.

Random, blinded, unique ID numbers will be assigned to specimens at each time point (baseline and post-treatment: 12 months and 18 months) and will be distributed with the PID number. All specimens will be labeled with the unique specimen number (XXXX), date (DD-MM-YY) and product code (N) using a permanent, waterproof marker. Laboratories will be blinded from distinguishing participant information and visit point but this information will be kept available in a password protected electronic log at each site to indicate which specimen number belongs to which participant and at what visit and at the Coordinating Center.

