- 8.2.3 **Differences in the activation status of NF-kB by assessing levels of total and phospho-p65 and cytoplasmic to nuclear translocation of phospho-p65 which is likely to be affected by aspirin** (baseline, 12 and 18 months). Fractionation and Western blot for the p65 NF-kB family member: Using esophageal squamous and neosquamous mucosal biopsies taken before and after treatment with aspirin, levels of phospho-p65 and total p65 will be determined by Western blot and quantitated by densitometry. We will then evaluate the cytoplasmic to nuclear translocation of phospho-p65 protein as previously described by us. Nuclear extracts will be isolated from tissues using the NE-PER Nuclear and Cytoplasmic Extraction kit (Thermo Fisher Scientific, Rockford, IL) per manufacturer's instructions. Blots will be probed with antibodies to phospho-p65 and total p65. Tubulin and transcription factor IIB (TFIIB) antibodies will be used to assure the purity of the cytoplasmic and nuclear subcellular fractions, respectively.
- 8.2.4 **Differences in the prostanoid marker, prostaglandin E2, and prostaglandin synthases** (baseline, 12 and 18 months), which are known to respond to aspirin and to correlation with clinicopathological factors in the esophageal cancer (14, 24). PGE2 was previously shown to be reduced in Barrett's mucosa in response to a combination of acid inhibition and high-dose (but not low dose) aspirin. Endogenous eicosanoids will be extracted from snap frozen biopsies and analyzed as we have previously described (25). Immediately following isolation, biopsies will be placed in individual vials containing 5 µg/mL aqueous indomethacin, instantly snap frozen in liquid nitrogen and maintained in liquid nitrogen. Using this regimen, measured PGE2 reflects the actual concentration in vivo (26).
- 8.2.5 **Differences in the expression of proinflammatory cytokines known to induce activation of NFkB, i.e., TNF $\alpha$ , IL-1 $\beta$ , IL-6, IL-10, IL-17A, IL-23** will be measured (baseline, 12 and 18 months). These inflammatory mediators have been implicated in the pathogenesis of BE and esophageal adenocarcinoma. Snap frozen biopsies will be homogenized in lysis buffer and endogenous IL-1 $\beta$ , IL-6, IL-10, IL-17A, IL-23, and TNF $\alpha$  will be simultaneously measured utilizing a human Bio-Plex customized multiplex kit (Bio-Rad) and the Bio-Plex 200 System as we have previously described (27).

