### 10.3 Shipping Instructions

Biopsies taken for research specimens (A1, B1, C1) will be placed in formalin and shipped overnight to the MD Anderson (MDACC) Coordinating Center for further processing. MDACC Research Histology Core will process and paraffin-embed the samples, and then cut one H & E and 20 unstained slides. [name] or his designee will provide a diagnosis for these samples (confirmed absence of Barrett's metaplasia or dysplasia, or presence of Barrett's metaplasia or dysplasia). Biopsies A2, B2 and C2 will be shipped the 3rd week of each month.

Biopsies taken for formalin fixation and paraffin embedding will be placed in prefilled 10% neutral buffered formalin (Azer Scientific 10 ml prefilled in 20 ml containers supplied by the coordinating center). Containers will be wrapped in parafilm, placed in plastic bags, bags sealed and shipped overnight to the coordinating center at the address listed below.

Frozen specimens will be batch shipped on dry ice monthly to the Coordinating Center at MDACC.

- All tissue samples must be kept frozen (-80°C or below) after preparation and until shipment is initiated.
- Wrap the frozen samples in bundles using an elastic band or place samples in appropriate sample storage box and place in a plastic freezer bag.
- Use newspaper or other similar material to insulate the bagged sample bundles from direct contact with the dry ice.
- Shipping containers (e.g., outer foam/cardboard shipping boxes) should be insulated, filled with dry ice and sealed with tape at the time the shipment is made. The shipping labels supplied should be affixed firmly to the outside of each container.
- All samples must be shipped in accordance with local biohazard requirements. Please refer to your institutional policy for biohazard labeling and packaging for shipment of hazardous and infectious human samples. If sealed biohazard containers are used, DO NOT place dry ice inside these containers. Place dry ice outside the containers only. Include a minimum of 10 kg dry ice when shipping by overnight express. Record the estimated weight of the dry ice used per box.
- Shipments should not be made on Friday or the day prior to a public holiday.

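### The PGE2 biopsies have two conflicting handling rules: Section 8.2.4 puts them straight into indomethacin vials, while Section 10.2 washes them in saline first and names no indomethacin

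*Combined protocol and SAP*

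**What the plan says.** Section 8.2.4 describes how tissue for the eicosanoid assay is to be handled. On timing it says: "Immediately following isolation, biopsies will be placed in individual vials containing". The vial content, at a strength of 5 µg/mL, and the freezing come next: "aqueous indomethacin, instantly snap frozen in liquid nitrogen and maintained in liquid nitrogen". It then says that, with this regimen, measured PGE2 "reflects the actual concentration in vivo (26" (the closing number is a literature citation).

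Section 10.2 lists the biopsies by level and planned use. At each of the three levels, biopsies 5, 6 and 7 (A5-A7, B5-B7, C5-C7) are marked as flash frozen and assigned to PGE2 and proinflammatory cytokines. Below the table, A1, B1 and C1 go into formalin and A2, B2 and C2 into RNAlater. Everything else follows one rule: "The remainder of the biopsies will be washed in phosphate buffered saline, each biopsy placed in a cryovial then placed in liquid nitrogen".

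Section 10.2 does point back to Section 8, but only for the assays: "Types of assay conducted for each biopsy specimen are described in Section 8". For the cytokines, which share the PGE2 biopsies, Section 8.2.5 says "Snap frozen biopsies will be homogenized in lysis buffer and endogenous" cytokines measured; it names no indomethacin.

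**The concern.** PGE2 at 12 and 18 months is a named secondary endpoint in the Schema. Section 8.2.4 attaches its statement about in vivo levels to a particular way of handling the tissue. The section that tells sites how to handle specimens puts a wash between isolation and freezing and leaves out the indomethacin.

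Two things are at stake. First, tissue handled by Section 10.2 alone would not meet the condition that the protocol states for its own measurement, and a biopsy cannot be handled again once it is frozen. Second, a site working from Section 8.2.4 and a site working from Section 10.2 could each claim to be following the protocol. Section 13.3 lists ten sites, and the randomization in Section 13.2 uses permuted blocks with no stratification by site stated. The plan therefore does not guarantee that a difference in handling between sites would be balanced across two arms of about 20. A change of handling between visits would enter the change from baseline.

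**Working it through.** The plan gives no power or precision figure for PGE2, so the check is a comparison of texts plus a count of biopsies.

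**The two procedures side by side**

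| Step | Section 8.2.4 (PGE2) | Section 10.2 (all biopsies not in formalin or RNAlater) |
|---|---|---|
| Straight after isolation | Into an individual vial | Washed in phosphate buffered saline |
| Medium in the vial | 5 µg/mL aqueous indomethacin | None named; cryovial |
| Freezing | At once, liquid nitrogen | Liquid nitrogen, after the wash |
| Storage | Kept in liquid nitrogen | "Vials will be stored at a temperature of" -80°C |

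**Does the Section 10.2 rule cover the PGE2 biopsies?** Yes. The only biopsies handled otherwise are numbers 1 and 2 at each level. Numbers 5 to 7 are not exempted.

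**Is indomethacin brought in from elsewhere?** No. It appears only in Section 8.2.4. It is absent from the biopsy procedures in Section 7 and from Sections 10.2 to 10.4. Section 10.2 names the medium for the biopsies that have one (formalin, RNAlater). Its reference to Section 8 concerns types of assay, not handling.

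**Count per endoscopy, from the Section 10.2 table**

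- Per level: 1 formalin + 2 RNAlater + 2 frozen for CDX2 + 1 for p65 + 3 for PGE2 and cytokines = 9.
- Three levels: 3 × 9 = 27, which reproduces the total of research biopsies in Section 7.2.2.
- Under the saline-wash rule: (2 + 1 + 3) × 3 = 18.
- For PGE2 and cytokines: 3 × 3 = 9, that is 9/27 = 33% of the research biopsies and 9/18 = 50% of those washed.

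**CDX2.** Section 8.1 sets no handling condition before freezing that conflicts with Section 10.2, so the primary endpoint is outside this point.

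**The case against.** The strongest reply is that Section 8.2.4 is specific to one assay and Section 10.2 is general. A cryovial need not be empty, so the specific text could add indomethacin to the general rule. This has some force for the indomethacin, where Section 10.2 is silent. It does not settle the wash, which is a positive instruction and cannot come before a step described as immediate.

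A second reply is that working instructions lie outside the protocol. Kits with collection and handling instructions are required (Sections 7.6 and 10.2), and tissue procurement is standardized in pre-trial discussions (Section 3.3, Study Assessments). These may well settle the matter in practice. Their content is not shown, and they would not remove the contradiction from the protocol. This does mean that a reader should not infer that sites will omit the indomethacin.

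A third reply concerns consequence, and it largely stands. The endpoint is a difference between randomized, blinded arms, and the laboratories are blinded to participant and visit. One rule applied to everyone would be the same in both arms at all visits, and such a comparison does not strictly need PGE2 to equal its in vivo level. Added noise or attenuation is possible, but nothing in the documents sizes it.

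Storage is a minor difference. Section 10.3 says "All tissue samples must be kept frozen (-80°C or below) after preparation and until shipment is initiated", which allows liquid nitrogen until shipment, and has the Coordinating Center store samples under appropriate conditions.

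**Conclusion.** The contradiction is real, and the protocol should not stand as written on this point. By Section 10.2, 9 of the 27 research biopsies at each endoscopy, all of those assigned to PGE2, are washed before freezing with no indomethacin named. Section 8.2.4 requires the opposite and ties its in vivo statement to doing so. The conclusion rests on the protocol text alone; the kit instructions were not available.

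Three stronger readings are tempting and are not supported:

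- **That the PGE2 endpoint is invalid or biased.** Section 8.2.4 says what its regimen achieves. It does not say that other handling gives unusable values. Neither size nor direction of an effect can be computed, for PGE2 itself or for the difference between arms.
- **That a known number of specimens is affected.** Multiplying out gives 9 × 3 endoscopies × 40 participants = 1,080, but these would be specimens allocated to the two assays, not specimens shown to be mishandled. Nor is it the trial's total: baseline research biopsies precede randomization (Section 10.2), and Section 13.4 plans CDX2 measurement in non-randomized patients too.
- **That storage at -80°C is a second conflict of equal weight.** It is a difference in wording to tidy up along with the rest.

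**What to change.** Reconcile Section 8.2.4, Section 10.2 and the kit instructions into one written procedure for the PGE2 biopsies, used at every site and visit. It should state whether there is a wash, whether the vial holds indomethacin, and one storage condition; Sections 10.3 and 10.4 should agree with it.

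Before the procedure is fixed, the laboratory should confirm that it suits the cytokine assay, since both assays draw on the same three biopsies per level. If it does not, the Section 10.2 table should designate which of the three go to each assay.

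The documents do not show which text is intended, so the wording depends on the sponsor's answer:

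- If the Section 8.2.4 regimen is intended, exempt the PGE2 biopsies from the saline-wash rule in Section 10.2.
- If the Section 10.2 handling is intended, remove the in vivo statement from Section 8.2.4 or support it separately.

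The cost is small: wording in a few sections and the kit instructions, and no extra biopsies. Indomethacin vials need adding only if that regimen is chosen and the kits do not already hold them. The one real downside comes with splitting: each assay would then have 1 or 2 biopsies per level instead of 3.

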### 10.3 Shipping Instructions

Biopsies taken for research specimens (A1, B1, C1) will be placed in formalin and shipped overnight to the MD Anderson (MDACC) Coordinating Center for further processing. MDACC Research Histology Core will process and paraffin-embed the samples, and then cut one H & E and 20 unstained slides. [name] or his designee will provide a diagnosis for these samples (confirmed absence of Barrett's metaplasia or dysplasia, or presence of Barrett's metaplasia or dysplasia). Biopsies A2, B2 and C2 will be shipped the 3rd week of each month.

Biopsies taken for formalin fixation and paraffin embedding will be placed in prefilled 10% neutral buffered formalin (Azer Scientific 10 ml prefilled in 20 ml containers supplied by the coordinating center). Containers will be wrapped in parafilm, placed in plastic bags, bags sealed and shipped overnight to the coordinating center at the address listed below.

Frozen specimens will be batch shipped on dry ice monthly to the Coordinating Center at MDACC.

- All tissue samples must be kept frozen (-80°C or below) after preparation and until shipment is initiated.
- Wrap the frozen samples in bundles using an elastic band or place samples in appropriate sample storage box and place in a plastic freezer bag.
- Use newspaper or other similar material to insulate the bagged sample bundles from direct contact with the dry ice.
- Shipping containers (e.g., outer foam/cardboard shipping boxes) should be insulated, filled with dry ice and sealed with tape at the time the shipment is made. The shipping labels supplied should be affixed firmly to the outside of each container.
- All samples must be shipped in accordance with local biohazard requirements. Please refer to your institutional policy for biohazard labeling and packaging for shipment of hazardous and infectious human samples. If sealed biohazard containers are used, DO NOT place dry ice inside these containers. Place dry ice outside the containers only. Include a minimum of 10 kg dry ice when shipping by overnight express. Record the estimated weight of the dry ice used per box.
- Shipments should not be made on Friday or the day prior to a public holiday.

- An inventory listing of all the samples must be included in the shipment. The inventory listing should contain the following information from each sample label: protocol number, patient number, patient initials and date and time of collection, along with any other pertinent information. Before placing in the shipping container, put the inventory list in a plastic bag for protection.

Samples will be shipped in containers provided and according to instructions provided by the Coordinating from collaborating Institutions to the following location:

[name]  
UT MD Anderson Cancer Center  
Department of Gastroenterology, Hepatology and Nutrition  
[name]  
Houston, Texas 77030-4900  
[contact]  
Back-up [contact]  
[contact]  
Email: [[contact]](mailto:[contact])

The Coordinating Center will be notified via e-mail when samples are shipped, so if samples are delayed or lost, tracking may be initiated by the sending site. Sample shipment forms are included with shipments. These data forms describe the date of sample receipt, and availability of sample, along with tracking information. The Coordinating Center will evaluate the sample condition on arrival, enter the sample numbers in the database, verify samples shipped match samples sent, and store at appropriate conditions until shipment to analytical labs.

All samples will be shipped in compliance with the International Air Transport Association (IATA) Dangerous Goods Regulations.

